1. OBJECTIVES

The overall objective of this prospective, single-arm, open-label, non-randomized, Phase IIA trial is to determine the immunogenicity of a prime and deferred-booster dosing schedule (prime dose at baseline and deferred-booster dosing at 24 months and optional booster at 30 months) of a nonavalent prophylactic HPV vaccine (GARDASIL 9) among 9-11 year-old girls and boys.

1.1 Primary Objectives

- To determine the persistence and stability of serologic geometric mean titer (GMT) of HPV 16/18 between 6, 12, 18, and 24 months after the prime dose and prior to the administration of the second dose.

1.2 Secondary Objectives

- To determine the persistence and stability of serologic GMT of HPV types 6/11/31/33/45/52/58 between 6, 12, 18, and 24 months after prime dose and prior to the administration of the second dose and
- To assess safety and reactogenicity to each vaccine dose.

2. BACKGROUND

2.1 HPV infection

Persistent infection with human papillomavirus (HPV) can cause cervical cancer in women as well as genital warts, anogenital and oropharyngeal cancers in both women and men. More than 150 HPV types have been identified. High-risk types (e.g., types 16 and 18) can cause low-grade cervical cell abnormalities, high-grade cervical cell abnormalities that are precancerous to cancer, and cervical cancers [1]. Essentially all cervical cancers are attributable to high-risk HPV types [2], and approximately 70% of cervical cancer cases worldwide are caused by types 16 and 18 [3]. In addition to cervical cancer, HPV infection can lead to some other anogenital cancers as well as cancer of the oropharynx [4, 5]. Low-risk types (e.g., types 6 and 11) can cause benign or low-grade cervical cell changes, genital warts, and recurrent respiratory papillomatosis [6].

2.2 HPV vaccine

Three HPV vaccines are licensed for use in the U.S. including the bivalent vaccine that protects against HPV types 16 and 18, quadrivalent vaccine that protects against HPV types 6, 11, 16, and 18, and the recently approved nonavalent vaccine that protects against HPV types 6/11/16/18/31/33/45/52/58. The available HPV vaccines provide an opportunity to decrease the burden of HPV-attributable cancers and genital warts.

The HPV vaccines have been given as a series of three injections over 6 months (consisting of a priming injection followed by booster injections at 2 and 6 months after the priming injection). In addition to the currently approved 3-dose schedule, a 2-dose schedule has recently been recommended by the U.S. Centers for Disease Control and Prevention (CDC) for 9-14 year-old. The U.S. Food and Drug Administration (FDA) has also recently approved adding a 2-dose schedule (consisting of a priming injection followed by 1 booster injection 6-12 months later) for the nonavalent HPV vaccine for children ages 9 through 14 years. At present, the cost of these regimens and logistical difficulties associated with administering 2-3 doses over 6-12 months make it impractical to vaccinate preadolescent and young women in developing countries [7]. In the U.S., recent CDC data suggests that only 37% of the target-age adolescents complete the recommended 3-dose vaccine series [8] with most receiving vaccine doses outside of the recommended windows of the prescribing schedule.

2.3 Rationale

Recent data showed that serologic responses following two doses of the quadrivalent and bivalent HPV vaccine are non-inferior to those following three doses of the respective vaccines [9, 10]. Consequently, the Strategic Advisory Group of Experts on immunization for the World Health Organization recommended a two-dose regimen for girls aged <15 years in 2014 (http://www.who.int/immunization/sage/meetings/2014/april/report_summary_april_2014/en/). This was followed by the recent (October 2016) FDA approval and CDC's recommendation of the 2-dose schedule for children ages 9 through 14 years (<https://www.cdc.gov/media/releases/2016/p1020-hpv-shots.html>). Furthermore, studies suggest that HPV vaccine may have the potential to achieve efficacy with only one dose because the HPV vaccines employ virus-like particles, which induce strong immunogenicity secondary to repetitive antigen display [11]. Kreimer et al. [12] evaluated the vaccine efficacy of fewer than three doses of the bivalent HPV vaccine in women randomized in a Phase III clinical trial in Costa Rica and showed that the vaccine efficacy against 12-month persistent HPV16/18 infection was similarly high among women who received, one, two, or the recommended three doses of the vaccine. A follow-up study investigated the magnitude and durability of serologic response to the bivalent vaccine [13] in four vaccinated groups: one dose, two-doses separated by one month, two-doses separated by six months, and three scheduled doses. The analysis showed that at four years, 100% of the women in all dose groups remained seropositive for HPV16/18. HPV16/18 geometric mean titers (GMT) were at least 24 and 14 times higher in the two-dose group and 9 and 5 times higher in the one-dose group in comparison with those in women with the natural infection. In addition, the antibody levels following one dose remained stable from month 6 through month 48. These data suggest that one dose of HPV vaccine may induce long-term protection.

Data comparing immunogenicity of 1 vs. 2 vs. 3 doses of the quadrivalent HPV vaccine (Gardasil) in a trial among ~17,000 girls ages 10-18 years in India suggests that single dose recipients had HPV 16/18/6/11 antibody titers higher than the seropositivity cut-off levels of titers defined for natural infection, and that these titers in single-dose recipients were stable and persistent up to 36 months post-vaccination [14]. The antibody avidity responses in single dose recipients of the HPV vaccine were non-inferior to similar responses in 2-dose and 3-dose recipients up to 36 months post-vaccination. Furthermore, as an early indicator of efficacy by dosing groups, in the subset of sexually active participants for whom cervical DNA was available for testing, the frequency of incident HPV infections were similar across the different dose groups, and no persistent HPV16 or HPV18 infections were reported in any of the dose groups.

It is not known whether a single dose of the nonavalent HPV vaccine will exert persistent immunogenicity similar to the bivalent or quadrivalent HPV vaccines. Because vaccination with a single vaccine dose could simplify the logistics and reduce costs of vaccination in the US and the developing world, it is important to determine the persistence of the immune titers of a single dose of nonavalent vaccine. In addition, it is anticipated that the vaccination pattern of the nonavalent HPV vaccine will be similar to the previous generations of the HPV vaccines. Therefore, it is also important to understand the immunogenicity of the nonavalent HPV vaccine to determine whether immunization occurring outside the recommended window would induce protection similar to the recommended schedule.

Here, we propose a prospective, single-arm, open-label, non-randomized, Phase IIA trial of a nonavalent prophylactic HPV vaccine (GARDASIL 9) to assess the immunogenicity of an alternative schedule (prime dose at baseline and deferred-booster dosing at 24 months, with an optional booster to be offered at 30 months) among 9-11-year-old girls and boys. The booster at 30 months is now optional because after this study began, CDC changed their recommendation for HPV vaccination from 3 to 2 doses for people starting their series before the 15th birthday

(<https://www.cdc.gov/mmwr/volumes/65/wr/mm6549a5.htm>; <https://www.cdc.gov/hpv/hcp/2-dose/clinician-faq.html>). Participants from the youngest of the licensed age groups (9-11 years) are selected for this proof-of-principle study given the potential for younger age children to mount higher immune titers [15], and the fact that immune responses to a single dose or two doses of the HPV vaccines among girls aged 9-14 years appear to be comparable to antibody responses of 3 doses in young women 15-25 years old [9]. The study hypothesis is that a single dose of the nonavalent HPV vaccine will induce persistent and stable serological responses for up to 24 months to all 9 vaccine HPV types in girls and boys 9-11 years of age.

3. SUMMARY OF STUDY PLAN

This is a prospective, single-arm, open-label, non-randomized, Phase IIA trial of a nonavalent prophylactic HPV vaccine (Gardasil 9) to assess the immunogenicity of a deferred-booster schedule (prime dose at baseline and deferred-booster dosing at 24 months and optional booster at 30 months) among 9-11 year-old girls and boys.

Healthy young, medically well girls and boys ranging from 9-11 years of age referred by their practitioners for HPV vaccination will be recruited from institution pediatric clinics and collaborating clinics. Detailed inclusion and exclusion criteria are described in sections 4.1 and 4.2.

Participants will undergo a pre-study screening evaluation. The legal representative(s) of the participants will be required to sign the informed consent form and medical records release form. Participants will be asked to sign the assent form. Participants and their legal representative(s) will be interviewed for past medical history (including age of menarche) and concomitant medication use. Participants will be assessed for height, weight, and vital signs (temperature, pulse, and blood pressure). Participants will be evaluated for baseline signs and symptoms. Urine pregnancy test will be performed on female participants who have started menstrual periods. The legal representative(s) will complete a questionnaire to collect information on the participant's parental education attainment and household income.

Eligible participants and their legal representative(s) will return to the clinic for a baseline visit. This visit may be combined with the prestudy screening evaluation visit. If the baseline visit occurs more than 30 days from the screening visit, participants will be reassessed for weight and vital signs. Adverse events and concomitant medications will be reviewed and age at menarche and urine pregnancy test, if applicable, will be reassessed at the baseline visit unless it occurs on the same day as the screening visit. If the participant is pregnant, she will be considered off-study and not undergo additional study procedures, including vaccination. A blood sample will be collected from the participants and serum separated and stored at -80°C. Participants will be offered topical anesthetic cream to be applied to the blood collection site prior to the collection. Following the blood collection, participants will receive the priming injection of Gardasil 9 and be observed in the clinic for at least 15 minutes.

Participants and legal representatives will be instructed to record adverse events for two weeks following each injection which will then be mailed back to the study office in a pre-stamped and addressed envelope.

Participants and their legal representatives will return to the clinic at 6, 12, 18, 24, and 30 months after the priming injection of Gardasil 9. These study visits will occur +/- 2 weeks of the scheduled times unless significant scheduling problems arise.

For the months 6, 12, and 18 visits, participants will be assessed for adverse events, concomitant medications, menarche, if applicable. Weight and height will be assessed at the month 12 visit. A blood sample will be collected from the participants at each visit and serum separated and stored at -80°C.

Similarly, participants will be offered topical anesthetic cream to be applied to the blood collection site prior to the collection.

For the months 24 and 30 visits, participants will be assessed for vital signs, adverse events, concomitant medications, and menarche and urine pregnancy test, if applicable. If the participant is pregnant, she will be considered off-study and not undergo additional study procedures, including vaccination. Weight and height will be assessed at the month 24 visit. A blood sample will be collected from the participants at each visit and serum separated and stored at -80°C. Similarly, participants will be offered topical anesthetic cream to be applied to the blood collection site prior to the collection. Following the blood collection at the month 24 visit, participants will receive the booster injection of Gardasil 9 and be observed in the clinic for at least 15 minutes. The booster injection of Gardasil 9 at the month 30 visit will be offered but is optional based on the latest CDC recommendation. Vital signs and urine pregnancy test will not be required for participants who do not receive the 3rd vaccine injection at the Month 30 visit.

Participants and their legal representatives will be contacted once a month and also within two weeks prior to each visit in their preferred method of contact to promote participant retention. They will be reminded during each contact that the subject should not receive the HPV vaccine from any provider outside the study. Additionally, we will provide subjects/legal representatives with wallet cards to indicate that the subject is participating in a research study and include the dates the HPV vaccine injection was given. We will also send a letter to the subject's primary care provider.

Participants will be followed for 2 weeks after completion of the last Gardasil 9 injection for safety evaluation.

We plan to accrue a total of 143 girls and 57 boys. With an estimated attrition rate of 30%, we anticipate having at least 100 girls and 39 boys completing the 30 month visit.

In addition, participants and their legal representatives may be contacted in the future if they have consented to allow for the possibility of re-consenting for additional serologic testing after the trial is completed.

4. PARTICIPANT SELECTION

4.1 Inclusion Criteria

- 4.1.1 Healthy, medically well girls and boys
- 4.1.2 Ages 9-11 at enrollment (on/after the 9th birthday but before the 12th birthday at enrollment)
- 4.1.3 Ability to understand and the willingness to sign a written informed consent document by the legal representative(s) of the participant
- 4.1.4 Ability to understand and the willingness to sign a written assent document by the participant

4.2 Exclusion Criteria

- 4.2.1 Previous vaccination against HPV
- 4.2.2 The use of any investigational agent within 30 days preceding the first dose of the study vaccine or subsequent participation in another clinical trial at any time during the study period, in which the subject will be exposed to an investigational product

- 4.2.3 Chronic administration of immunosuppressive agents or other immune-modifying drugs or chemotherapeutic agents within six months prior to the first vaccine dose. Use of inhaled steroids, nasal sprays, and topical creams for small body areas is allowed
- 4.2.4 Receiving active treatment for cancer or an autoimmune condition
- 4.2.5 Confirmed or suspected immunosuppressive or immunodeficient condition
- 4.2.6 Known bleeding disorders that preclude intramuscular injection (e.g., on anticoagulants or thrombocytopenia)
- 4.2.7 Acute or chronic, clinically significant pulmonary, cardiovascular, hepatic or renal dysfunction, which in the opinion of the investigator precludes administration of the study vaccine
- 4.2.8 History of allergic reactions attributed to compounds of similar chemical or biologic composition of GARDASIL 9, including yeast allergy
- 4.2.9 Are pregnant

4.3 Inclusion of Women and Minorities

HPV vaccines have been approved for use in both girls and women as well as in boys and men between 9 and 26 years of age. This study focuses on the youngest of the licensed age groups (9-11 years), including both girls and boys, because of the potential for younger age children to mount higher immune titers. Members of all races and ethnic groups are eligible for this trial.

4.4 Recruitment and Retention Plan

For University of Arizona, study participants will be primarily recruited from the University of Arizona pediatric clinics and Pima County Health Department Clinics. For University of California Los Angeles, study participants will be primarily recruited from outpatient offices of the UCLA Community Physician Network.

Additional recruitment methods include community physician referrals, the institutional websites postings, community outreach activities, advertisement from different media outlets, and outreach to local schools. Recruitment materials such as brochures or flyers may be developed to help recruit study participants.

The study team will provide a friendly and comfortable study setting for participants and their legal representative(s) from initial contact through the completion of the study. Demands upon the subjects will be minimized to foster comfort while preserving the research goals. Wherever possible, flexibility will be built into the study schedule to promote compliance. Participants and their legal representatives will be contacted once a month and also within two weeks prior to each visit in their preferred method of contact to promote participant retention.

5. AGENT ADMINISTRATION

Agent will be administered on an outpatient basis. Reported adverse events (AEs) and potential risks are described in Section 6.2.

5.1 Dose Regimen and Dose Groups

- The study agent is Gardasil 9.
- Participants will receive the priming injection at baseline, a booster injection at 24 months and an optional booster injection at 30 months after the priming injection.

5.2 Gardasil 9 Administration

- Shake well before use.
- Administer the entire dose of Gardasil 9 (0.5 ml) intramuscularly in the deltoid region of the upper arm or in the higher anterolateral area of the thigh.
- Participants should be seated or lying down during administration.
- Participants should be observed in the clinic for at least 15 minutes following the administration of Gardasil 9.

5.3 Run-in Procedures

Not applicable.

5.4 Contraindications

Hypersensitivity, including severe allergic reactions to yeast (a vaccine component), or after a previous dose of GARDASIL 9 or GARDASIL.

5.5 Concomitant Medications

All medications (prescription and over-the-counter), vitamin and mineral supplements, and/or herbs taken by the participant will be documented on the concomitant medication CRF and will include: 1) start and stop date, dose and route of administration, and indication. Medications taken for a procedure (*e.g.*, biopsy) should also be included. Participants and their legal representatives will be reminded to refrain from non-study HPV vaccination during their study participation. If a subject receives an HPV vaccine outside the context of the study, he/she will be taken off study. This information will be captured in the source document and on the Concomitant Medication CRF and a comment addressing this will be added to the Agent Interruption CRF. Other vaccines received by the participants will be considered to be concomitant medications and will also be captured on the Concomitant Medications CRF.

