Serious adverse events (SAEs) were collected throughout the entire study period (range one to 48 months post-last dose) for the six integrated clinical studies with Gardasil 9. Of the 13,236 individuals who were administered Gardasil 9 and had safety follow-up, 305 reported an SAE, representing 2.3% of the population. Five reported at least one SAE that was determined to be vaccine-related: pyrexia, allergy to vaccine, asthmatic crisis, headache, and tonsillitis. There were no vaccine-related deaths among individuals administered Gardasil 9 in the clinical studies.

In all of the clinical trials with Gardasil 9, subjects were evaluated for new medical conditions potentially indicative of a systemic autoimmune disorder. In total, 2.4% (321/13,234) of Gardasil 9 recipients reported new medical conditions potentially indicative of systemic autoimmune disorders, which were similar to rates reported following Gardasil, AAHS control, or saline placebo in historical clinical trials.

The safety of Gardasil 9 when administered concomitantly with Menactra (Meningococcal [Groups A, C, Y and W-135] Polysaccharide Diphtheria Toxoid Conjugate Vaccine) and Adacel (Tetanus Toxoid, Reduced Diphtheria Toxoid and Acellular Pertussis Vaccine Adsorbed [Tdap]) was evaluated in a randomized study of 1,241 boys (n = 620) and girls (n = 621) with a mean age of 12.2 years. Of the 1,237 boys and girls vaccinated, 1,220 had safety follow-up for injection site adverse reactions. The rates of injection site adverse reactions were similar between the concomitant group and nonconcomitant group (vaccination with Gardasil 9 separated from vaccination with Menactra and Adacel by one month) with the exception of an increased rate of swelling reported at the injection site for Gardasil 9 in the concomitant group (14.4%) compared to the non-concomitant group (9.4%). The majority of injection site swelling adverse reactions were reported as mild to moderate in intensity.

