7.3 Evaluation During Study

Participants and legal representatives will be instructed to record adverse events for two weeks following each injection which will then be mailed back to the study office in a pre-stamped and addressed envelope.

Participants and their legal representatives will return to the clinic at 6, 12, 18, 24, and 30 months after the priming injection of Gardasil 9. These study visits will occur +/- 2 weeks of the scheduled times unless significant scheduling problems arise.

For the months 6, 12, and 18 visits, participants will be assessed for adverse events, concomitant medications, menarche, if applicable. Weight and height will be assessed at the month 12 visit. A blood sample will be collected from the participants at each visit and serum separated and stored at -80°C. Similarly, participants will be offered topical anesthetic cream to be applied to the blood collection site prior to the collection.

For the months 24 and 30 visits, participants will be assessed for vital signs, adverse events, concomitant medications, and menarche and urine pregnancy test, if applicable. If the participant is pregnant, she will be considered off-study and not undergo additional study procedures, including vaccination. Weight and height will be assessed at the month 24 visit. A blood sample will be collected from the participants at each visit and serum separated and stored at -80°C. Similarly, participants will be offered topical anesthetic cream to be applied to the blood collection site prior to the collection. Following the blood collection at the month 24 visit participants will receive the booster injection of Gardasil 9. At the month 30 visit, a 3rd vaccine injection will be offered but is optional. Vital signs and urine pregnancy test are not

required for participants who do not receive the 3rd vaccine injection at the Month 30 visit. Participants should be seated or lying down during vaccine administration. Participants will be required to sit or lie down for 15 minutes after the vaccine injection to help prevent fainting and injuries caused by falls and be observed in the clinic for at least 15 minutes.

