11.1 Adverse Events

11.1.1 Reportable AEs

All AEs that occur after the informed consent is signed and baseline assessments are completed (including run-in) must be recorded on the AE CRF (paper and/or electronic) including whether or not they are related to study agent.

11.1.2 AE Data Elements:

The following data elements are required for adverse event reporting.

- AE verbatim term
- System Organ Class (SOC)
- Common Terminology Criteria for Adverse Events v4.0 (CTCAE) AE term
- Event onset date and event ended date
- Severity grade
- Attribution to study agent (relatedness)
- Whether or not the event was reported as a serious adverse event (SAE)
- Whether or not the subject dropped due to the event
- Outcome of the event

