13.7 Evaluation of Toxicity

All participants will be evaluable for toxicity from the time of their first dose of vaccine. Descriptive statistics of the type and frequency of all adverse events will be generated, including 95% confidence intervals.

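### Other vaccines given around a study dose are logged with dates, but the safety analysis does not use that record, so injection-site swelling attributed to a dose can be inflated by co-vaccination

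*Combined protocol and SAP*

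**What the plan says.** The secondary objectives (Section 1.2) include this one: "To assess safety and reactogenicity to each vaccine dose". Sections 8.2 and 13.5 repeat it. Section 7.3 sets the collection window: "Participants and legal representatives will be instructed to record adverse events for two weeks following each injection".

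On other vaccines, Section 5.5 says: "Other vaccines received by the participants will be considered to be concomitant medications and will also be captured on the Concomitant Medications CRF". For each concomitant medication the form takes "start and stop date, dose and route of administration, and indication". The exclusion criteria (4.2), the dose-delay rule (5.6) and the visit procedures (7.3) neither bar nor space non-HPV vaccines around a study injection.

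Beyond making every participant evaluable from the first dose, the whole analysis in Section 13.7 is this: "Descriptive statistics of the type and frequency of all adverse events will be generated, including 95% confidence intervals". It states no split by dose and none by co-vaccination. Section 13.5 adds that secondary analyses are done separately for girls and boys. Adverse event records carry an onset date and a five-level relatedness to the study agent (11.1.2, 11.1.4). They have no field for another vaccine.

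**The concern.** The plan collects a known source of extra reactions and then leaves it out of the analysis. In the co-administration study described in Section 6.2, the extra swelling was at the Gardasil 9 site itself. Sorting reactions by injection site therefore would not remove it. Nor would relatedness to the study agent, because swelling at that site will naturally be judged related.

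The trial has one arm, so no concurrent group shows what a dose does on its own. If the share of co-vaccinated children differs between doses, the swelling rates will differ between doses with no true dose effect. A reader could then credit or blame the deferred schedule. The gap applies to the baseline, month-24 and optional month-30 doses alike.

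**Working it through.** **Inputs from the documents**
- Swelling at the Gardasil 9 site with and without concomitant vaccines: 14.4% and 9.4%; 1,220 children had injection-site follow-up (6.2).
- Background swelling at ages 9–15: girls 47.8%, boys 26.9% (6.2). The documents do not explain why these exceed 9.4%, so both bases are used.
- Expected completers: 100 girls and 39 boys (13.3), used as a precision yardstick.

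**Input not in the documents**
- Share f of injections with another vaccine close by: assumed, 0 to 100%.

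**The plan's own precision figure.** Section 13.4 gives maximum exact 95% interval widths of 0.203 (n = 100) and 0.328 (n = 39). Clopper-Pearson over all counts gives 0.2034 and 0.3280, so both reproduce. They were written for the two-fold-change percentages but apply to any proportion.

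**Size of the co-vaccination effect.** Difference: 14.4 − 9.4 = 5.0 points. Ratio: 14.4/9.4 = 1.53. If the 1,220 children were split equally (an assumption, 610 each), the 95% half-width is 1.96 × √(0.144×0.856/610 + 0.094×0.906/610) = 3.6 points. The interval is then about +1.4 to +8.6 points.

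**Effect on an unseparated rate.** Additive scale: observed = base + f × 5.0. Ratio scale: observed = base × (1 + f × 0.53).

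| f | base 9.4%, additive | girls 47.8%, additive | boys 26.9%, additive | girls, ratio | boys, ratio |
|---|---|---|---|---|---|
| 25% | 10.65 | 49.05 | 28.15 | 54.2 | 30.5 |
| 50% | 11.9 | 50.3 | 29.4 | 60.5 | 34.1 |
| 100% | 14.4 | 52.8 | 31.9 | 73.2 | 41.2 |

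**Against sampling error, by sex as Section 13.5 requires.** The standard error is √(p(1−p)/n).
- Girls at 47.8%: √(0.478×0.522/100) = 5.0 points. The additive bias at f = 50% is 2.5 points, or 0.50 SE.
- Boys at 26.9%: √(0.269×0.731/39) = 7.1 points, so 2.5 points is 0.35 SE.
- At the 9.4% base the same 2.5 points is 0.86 SE for girls (SE 2.9) and 0.53 SE for boys (SE 4.7).

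The exact 95% interval is 4.2–16.4% for 9/100 (half-width 6.1 points) and 37.9–58.2% for 48/100 (half-width about 10). The largest additive bias, 5.0 points, is inside both. On the ratio scale the shift for girls at f = 50% is 60.5 − 47.8 = 12.7 points, which is outside. The documents do not say which scale carries over.

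**Between doses.** If f₁ and f₂ are the shares at two doses, the spurious additive difference is (f₂ − f₁) × 5.0. It runs from −5.0 to +5.0 points, and its sign is unknown because neither share is given.

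**The case against.** The strongest reply is that little depends on this. The endpoint is secondary and descriptive, and Section 13.7 plans no test between doses and no comparison with the Section 6.2 rates. Section 6.2 reports injection-site reaction rates as similar between the co-vaccinated and separated groups, with swelling the sole exception and mostly mild to moderate. It also says that swelling and erythema already rise with each successive dose, so a higher rate at dose 2 would not by itself point to the 24-month interval. Onset dates and relatedness give some help with systemic events and with reactions at another vaccine's own site. All of this stands, and it limits the point to a minor one.

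A reader might go further and infer that co-vaccination clusters at month 24, so that the deferred dose in particular will look worse. The documents do not support that. They give no co-vaccination rate at any dose. Participants will be about 11 to 14 years old at month 24, and the co-administration study had a mean age of 12.2. That was a randomised comparison, however, so its mean age says nothing about when these children receive other vaccines. Some enrol just short of 12, so the first dose is exposed too.

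The objection does not remove the gap. Relatedness cannot separate swelling at the Gardasil 9 site. Because successive doses already raise swelling, a rise at dose 2 could not be divided between dose number, interval and another vaccine.

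**Conclusion.** The point holds, as a minor one. Other vaccines may be given around any study dose, their dates are collected, and the safety analysis ignores them. Injection-site swelling attributed to a dose can be inflated by f × 5.0 points, at most about 5, if the difference in Section 6.2 carries over additively. With half the injections co-vaccinated and the Section 6.2 background rates, that is 0.5 SE or less in either sex. If the ratio carried over instead, the shift in girls could exceed the interval's half-width. The share and the scale are both assumptions.

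The documents do not support extending this to pain or erythema. For systemic events, and for reactions at another vaccine's own site, they give no figure. The primary immunogenicity analysis is not in question. A difference in swelling between doses should not be read as an effect of the schedule without a split by co-vaccination.

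**What to change.** In Section 13.7, state that adverse events in the 14 days after each dose will be tabulated by dose and by sex. Keep the overall rate as the main figure. Beside it, show the rates for injections with and without another vaccine inside a pre-stated window, taken from the Concomitant Medications CRF dates. Fourteen days either side would match the diary. The separated group in Section 6.2 was one month apart, so the window is a choice and should be fixed before the tables are produced.

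This changes only the analysis and asks for no change in when other vaccines are given.

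Costs:
- **Precision.** If half the injections are co-vaccinated, the maximum exact 95% interval width goes from 0.203 to 0.289 in girls (50 of 100) and from 0.328 to about 0.46 in boys (20 of 39). This is why the restricted rate should sit beside the overall rate and not replace it.
- **Capture.** The schedule of events (7.1) records concomitant medications at clinic visits only. Vaccines given soon after the month-24 dose are therefore picked up at month 30. Those given in the 14 days after the optional month-30 dose have no scheduled capture, unless the question is added to the existing follow-up contact.
- **Interpretation.** The split is not randomised, so it describes the two groups and does not prove that the other vaccine caused the difference.
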